7.1.5.3 Sym004 Dose-Modifications for Events other than Grade 3 Skin Toxicity

In the occurrence of hypomagnesemia Grade 4, refractory to iv magnesium-replacement therapy as specified in [Section 7.2.5](#), dosing of Sym004 may be delayed or reduced. The need for > 2 week dose delays or dose-reduction should be discussed with the Sponsor or designee if adequate improvement is not seen after the initial delay.

Sym004 will not be delayed for FOLFIRI-related toxicities. FOLFIRI dosing will be resumed in combination with the next scheduled Sym004 administration once related toxicities have resolved.

7.2 Other Drugs to be used in the Trial

7.2.1 FOLFIRI

The FOLFIRI regimen consists of:

- Irinotecan 180 mg/m² iv, infused over 60-90 minutes, concurrently with
- Folinic Acid (FA) 400 mg/m² iv, infused over 120 minutes, followed by

- 5-Fluorouracil (5-FU) 400 mg/m² iv bolus, then 2400 mg/m² 5-FU infused over 46 hours

This regimen is typically repeated every 2 weeks. For the purposes of this trial, FOLFIRI will be administered on the same schedule as Sym004 i.e. every second week (Day 1 and Day 15 of each 28 day cycle, ± 2 days).

7.2.1.1 FOLFIRI Delays and Dose-Reduction

On the planned day of treatment, FOLFIRI may be administered only if the following treatment criteria are met:

- ANC $\geq 1.5 \times 10^9/L$ (1500/mm³)
- Platelet count $\geq 100 \times 10^9/L$ (100,000/mm³)
- FOLFIRI-related gastrointestinal toxicity is \leq Grade 1

If any of the above criteria are not met, all components of FOLFIRI dosing will be delayed. If FOLFIRI administration is delayed subsequent dosing will be resumed in combination with a scheduled Sym004 administration.

In the event of toxicities other than those listed above, dose-adjustments of the components of FOLFIRI should be made independently, based on the toxicity observed.

Table 7 presents the recommended dose-reductions for each of the components of FOLFIRI for which dose-modifications will be allowed. If a dose-reduction exceeding that represented by Dose Level -3 is required for any agent, that agent should be discontinued.

Table 7 FOLFIRI Dose-Reductions

FOLFIRI Component	Dose Level			
	Initial Dose	-1	-2	-3
Irinotecan	180 mg/m ²	150 mg/m ²	120 mg/m ²	100 mg/m ²
5-FU Bolus	400 mg/m ²	200 mg/m ²	0 mg/m ²	0 mg/m ²
5-FU Infusion	2400 mg/m ² over 46-48 hours	2000 mg/m ² over 46-48 hours	1600 mg/m ² over 46-48 hours	1200 mg/m ² over 46-48 hours

Abbreviations: 5-FU, Fluorouracil

FOLFIRI guidelines for dose modifications and delays are provided (refer to Appendix 2). If other symptoms not discussed in Appendix 2 occur, the Sponsor or designee should be consulted.

General dosing considerations are as follows:

- If 5-FU/FA administration is delayed, irinotecan treatment must also be postponed, although Sym004 administration may continue without postponement

- If irinotecan administration is delayed, 5-FU/FA treatment must also be postponed, although Sym004 administration may continue without postponement
- No dose-reductions will be implemented for FA; however, FA will always be withheld when 5-FU is held
- In general, if a dose is reduced because of toxicity, it should not be re-escalated to the starting level. However, patients who require dose-reductions during a cycle for Grade 2 toxicity may, at the investigator's discretion, begin the following cycle at 1 dose level higher than the final dose level during that cycle
- If FOLFIRI is withheld because of toxicity for more than 1 cycle (approximately 28 days), FOLFIRI will be discontinued; Sym004 may be continued if the toxicity resulting in FOLFIRI discontinuation is not considered by the investigator to be related to Sym004.

For hypersensitivity reactions due to infusion of irinotecan or 5-FU, treatment should be administered as per institutional guidelines and/or at the discretion of the Investigator.

7.2.2 Order of Sym004 and FOLFIRI Administration

Sym004 and FOLFIRI administration will be initiated on Day 1 and Day 15 (\pm 2 days) of each 28 day cycle. The Sym004 infusion will be delivered first. The FOLFIRI regimen administration will commence no sooner than 1 hour following completion of Sym004 administration.

7.2.3 Prophylactic Treatment

7.2.3.1 Prophylactic Treatment for Infusion Reactions

There is an inherent risk for IRRs with the administration of mAbs. A premedication schedule will therefore be implemented for all patients treated.

Prior to the first 2 infusions of Sym004 (i.e. during Cycle 1) all patients will receive:

- Glucocorticoid therapy equivalent to 80-100 mg iv methylprednisolone, approx. 0.5 to 2 hours prior to the start of Sym004 infusion
- Antihistamine (H1 antagonist) equivalent to 25-50 mg iv diphenhydramine, approx. 0.5 hours prior to the start of Sym004 infusion

For infusion following the completion of Cycle 1, pre-medication is at the Investigators discretion. Premedication should be reinstated in the event of Grade \geq 3 IRR.

7.2.3.2 Prophylactic Treatment for Gastrointestinal Toxicities

To minimize the risk of gastrointestinal side-effects related to FOLFIRI and/or Sym004, all patients will receive:

- Prophylaxis for nausea and vomiting according to institutional standards

- Mandatory prophylaxis for diarrhea as shown in [Table 8](#). Loperamide therapy may be continued beyond end of Cycle 1 (C1) at the Investigator’s discretion.

Table 8 Mandatory Prophylaxis for Diarrhea

Treatment	Dose	Start	Stop
Loperamide	4 mg po prior to start of FOLFIRI 4 mg tid	C1/D1	C1/D2
	4 mg tid	C1/D2	C1/D3
	2 or 4 mg tid or qid as required	C1/D4	End of C1

Abbreviations: C1/D1, Day 1 of Cycle 1; po, per os; tid, three times per day; qid, four times per day

- 1) Loperamide may be continued beyond end of Cycle 1 (C1) at the Investigator’s discretion
- 2) If the patient is experiencing \geq G2 diarrhea continuation of loperamide therapy at 4 mg on an up to qid schedule is permissible.
- 3) These recommendations do not supersede the recommendations for treatment or prophylaxis of early diarrhea due to irinotecan nor do they alter the recommendations for dose reduction of 5-FU or irinotecan as specified in [Appendix 2](#).

7.2.3.3 Prophylactic Treatment for Skin Toxicity

All patients will receive mandatory prophylactic treatment for skin toxicities and may be continued beyond end of Cycle 2 (C2) at the Investigator’s discretion as described in [Table 9](#).

Table 9 Mandatory Prophylaxis for Skin Toxicities

Treatment	Dose	Start	Stop	Alternatives
SYSTEMIC THERAPY¹				
Minocycline or Doxycycline	1 × 100 mg/day 2 × 100 mg/day	C1/D1	End of C2 ²	In case of intolerance: 
 • First generation cephalosporins • Amoxicillin • Erythromycin • Limecycline
TOPICAL THERAPY				
Low potency steroid creams such as 
 • Alclometasone 0.05% • Desonide 0.05 % • Fluocinolone 0.01% 	2 × daily on face and chest	C1/D1	End of C2	
Moisturizer (creams or ointments)	3 × daily to hands, and after hand washing using fragrance-free soaps 2 × daily to rest the body	C1/D1	Continue	

Abbreviations: C1/D1, Day 1 of Cycle 1; C2, Cycle 2

- 1) If infection is suspected (yellow crusts, purulent discharge, painful skin/nares) obtain culture and change to oral antibiotic based on sensitivities
- 2) May be continued beyond end of Cycle 2 (C2) at the Investigator’s discretion

7.2.4 Treatment of Skin Toxicity

Recommendations for management of Grade 1 to 3 Sym004 induced skin toxicities, i.e. rash, xerosis, paronychia, pruritus, photosensitivity and fissures, are summarized in [Table 10](#) to [Table 15](#) below.

In the event that a patient experiences any Grade 4 skin toxicity, the patient must be withdrawn from Sym004 treatment.

It is strongly recommended that a dermatologist is consulted in the event of Grade 3 or 4 skin toxicity.

Table 10 Treatment of Rash

CTCAE Grade	Action with Sym004	Treatment

Grade 1 Papules and/or pustules covering < 10% BSA, which may or may not be associated with symptoms of pruritus or tenderness
	
Continue at the same dose
	
Topical: Face and Chest
 
 • Steroid creams of low potency (alclometasone 0.05%, desonide 0.05% or fluocinolone 0.01%), 2 × daily, 
Rest-of-body
 
 • Moisturizers, 2 × daily, rest of body 
Systemic¹:
 
 • Minocycline 100 mg/day or doxycycline 200 mg/day at least 4 weeks

Grade 2 Papules and/or pustules covering 10-30% BSA, which may or may not be associated with symptoms of pruritus or tenderness; associated with psychosocial impact; limited instrumental ADL
	
Continue at the same dose
 
If locally debilitating for the patient, consider to follow guidelines of dose-delay and dose-reduction as outlined in Table 6
	
Topical:
 
 • See Grade 1 
Systemic¹:
 
 • Minocycline 100 mg/day or doxycycline 200 mg/day for at least 4 weeks • 1 week course of oral steroid: Methylprednisolone 4 mg tablets: Day 1: 2-1-1-2, Day 2: 1-1-1-2, Day 3: 1-1-1-1, Day 4: 1-1-1, Day 5 1-0-1, Day 6: 1

Grade 3 Papules and/or pustules covering >30% BSA, which may or may not be associated with symptoms of pruritus or tenderness; limiting self-care ADL; associated with local superinfection with oral antibiotics indicated
	
Delay dose of Sym004, continue skin treatment and re-asses. Refer to Table 6 for further guidelines on dose-reduction
	
Topical:
 
 • See Grade 1 
Systemic¹:
 
 • See Grade 2

Abbreviations (in alphabetical order): ADL, activities of daily living; BSA, body surface area; CTCAE, The National Cancer Institute (NCI) Common Terminology Criteria for Adverse Events, Version 4.03

- 1) Alternatives in case of intolerance: First generation cephalosporins, amoxicillin, erythromycin or limecycline. If infection is suspected (yellow crusts, purulent discharge, painful skin/nares): Obtain culture and change to oral antibiotic based on sensitivities

Table 11 Treatment of Xerosis

CTCAE Grade	Action with Sym004	Treatment

Grade 1 <10% BSA and no associated erythema or pruritus
	
Continue at the same dose
	
Topical: Face
 
 Moisturizing cream or ointment¹, 2 × daily 
And
 
Body
 
 Ammonium lactate 6-12% cream, 2 × daily

Grade 2 10-30% BSA associated with erythema or pruritus; limited instrumental ADL
	
Continue at the same dose
 
If locally debilitating for the patient, consider to follow guidelines of dose-delay and dose-reduction as outlined in Table 6
	
Topical: Face
 
 Moisturizing cream or ointment¹, 2 × daily 
And
 
Body
 
 Ammonium lactate 12% cream or salicylic acid 3-6% cream or urea 10-20% cream, 2 x daily

Grade 3 >30% BSA associated with pruritus; limited self-care ADL
	
Delay dose of Sym004, continue skin treatment and re-asses. Refer to Table 6 for further guidelines on dose-reduction
	
Topical: Face
 
 Moisturizing cream or ointment¹, 2 × daily 
And
 
Body
 
 Ammonium lactate 12% cream or salicylic acid 3-6% cream or urea 10-20% cream, 2 × daily; and Eczematous areas: Topical steroid (e.g. triamcinolone acetonide 0.025%, desonide 0.05%, alclometasone 0.05%, fluticasone propionate 0.05%), 2 × daily

Abbreviations (in alphabetical order): ADL, activities of daily living; BSA, body surface area; CTCAE, The National Cancer Institute (NCI) Common Terminology Criteria for Adverse Events, Version 4.03

- 1) If prescription is not available, recommendation by pharmacist/dermatologist is acceptable

Table 12 Treatment of Paronychia

CTCAE Grade	Action with Sym004	Treatment

Grade 1 Nail fold edema or erythema; disruption of the cuticle
	
Continue at the same dose
	
Topical:
 
 Antibiotics (e.g. clindamycin 1%, erythromycin 1%) and Vinegar soaks (i.e. soaking fingers or toes in a 1:1 solution of white vinegar in water for 15 minutes every day 
And Systemic:
 
 Bacterial culture, oral antibiotic if infection confirmed

Grade 2 Localized intervention indicated; oral intervention indicated (e.g., antibiotic, antifungal, antiviral); nail fold edema or erythema with pain; associated with discharge or nail plate separation; limiting instrumental ADL
	
Continue at the same dose
 
If locally debilitating for the patient, consider to follow guidelines of dose-delay and dose-reduction as outlined in Table 6
	
Same as for Grade 1
 
And Topical:
 
 Silver nitrate application weekly (needs consultation with dermatologist or surgeon)

Grade 3 Surgical intervention or iv antibiotics indicated; limiting self-care ADL
	
Delay dose of Sym004, continue skin treatment and re-asses. Refer to Table 6 for further guidelines on dose-reduction
	
Same as for Grade 1
 
And
 
 Silver nitrate application weekly (needs consultation with dermatologist or surgeon) 
And
 
 Consider nail avulsion (needs consultation with dermatologist or surgeon)

Abbreviations (in alphabetical order): ADL, activities of daily living; BSA, body surface area; CTCAE, The National Cancer Institute (NCI) Common Terminology Criteria for Adverse Events, Version 4.03; iv, intravenous

Table 13 Treatment of Pruritus

CTCAE Grade	Action with Sym004	Treatment

Grade 1 Mild or localized; topical intervention indicated
	
Continue at the same dose
	
Topical:
 
 • Steroid (e.g. triamcinolone acetonide 0.025%, desonide 0.05%, alclometasone 0.05%, Fluticasone propionate 0.05%), 2 × daily 
or
 
 • Anti-pruritics (e.g. pramoxine 1%, doxepin 5% cream), 2 × daily

Grade 2 Intense or widespread; intermittent; skin changes from scratching (e.g., edema, papulation, excoriations, lichenification, oozing/crusts); oral intervention indicated; limiting instrumental ADL
	
Continue at the same dose
 
If locally debilitating for the patient, consider to follow guidelines of dose-delay and dose-reduction as outlined in Table 6
	
Same as for Grade 1
 
And
 
Systemic:
 
 • Oral antihistamines (diphenhydramine 25-50 mg; hydroxyzine 25 mg; fexofenadine 60 mg, 3 × daily

Grade 3 Intense or widespread; constant; limiting self-care, ADL or sleep; oral corticosteroid or immunosuppressive therapy indicated
	
Delay dose of Sym004, continue skin treatment and re-asses. Refer to Table 6 for further guidelines on dose-reduction
	
Same as for Grade 2

Abbreviations (in alphabetical order): ADL, activities of daily living; BSA, body surface area; CTCAE, The National Cancer Institute (NCI) Common Terminology Criteria for Adverse Events, Version 4.03

Table 14 Treatment of Photosensitivity

CTCAE Grade	Action with Sym004	Treatment

Grade 1 Painless erythema and erythema covering <10% BSA
	
Continue at the same dose
	
Topical:
 
 Broad spectrum sunscreen with an SPF of at least 15; need to be applied every 2 hours or more frequently if swimming or perspiring 
And
 
Systemic:
 
 Bacterial culture, oral antibiotic if infection confirmed

Grade 2 Tender erythema covering 10-30% BSA
	
Continue at the same dose
 
If locally debilitating for the patient, consider to follow guidelines of dose-delay and dose-reduction as outlined in Table 6
	
Same as for Grade 1
 
And
 
Topical:
 
 Corticosteroids (e.g. triamcinolone acetonide 0.025%, desonide 0.05%, alclometasone 0.05% cream, fluticasone propionate 0.05%), 2 × daily

Grade 3 Erythema covering >30% BSA and erythema with blistering; photosensitivity; oral corticosteroid therapy indicated; pain control indicated (e.g. narcotics or NSAIDs)
	
Delay dose of Sym004, continue skin treatment and re-asses. Refer to Table 6 for further guidelines on dose-reduction
	
Same as Grade 2

Abbreviations (in alphabetical order): ADL, activities of daily living; BSA, body surface area; CTCAE, The National Cancer Institute (NCI) Common Terminology Criteria for Adverse Events, Version 4.03; NSAID, nonsteroidal anti-inflammatory drugs; SPF, sun protection factor

Prophylaxis of fissures includes careful use of moisturizing creams and/or ointments 3 times a day and after handwashing, using only fragrance-free soaps. Should fissures begin to form, a stepwise approach outlined in [Table 15](#) should be followed.

Table 15 Treatment of Fissures

Treatment Step	Action with Sym004	Treatment
Step 1 Initiated at first occurrence	No action	Topical: 
 Thick moisturizers of zink oxide (13-40%) cream Liquid glues of cyanoacrylate to seal cracks
Step 2 If no improvement after 2 weeks from initiation of Step 1	No action	Topical: 
 Thick moisturizers of zink oxide (13-40%) cream under occlusion at night Salicylic acid 6% cream or ammonium lactate/lactic acid 12%
Step 3 If no improvement after 2 weeks from initiation of Step 2	Delay dose of Sym004 and re-assess. Discuss need for dose-reduction and/or further dose omissions with Sponsor or designee	Continue local treatment as described in Step 2

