7.1.5.2 Sym004 Dose-Modifications for Skin Toxicity

The infusion of Sym004 must be paused in the event of a Grade 3 skin toxicity, by delaying the dose of Sym004 resulting in a period of approximately 28 days between 2 Sym004 administrations.

If Sym004 is paused, all per protocol scheduled assessments must be done and FOLFIRI will be administered according to the planned schedule and [Section 7.2.1](#).

Sym004 dosing will subsequently be resumed in combination with a scheduled FOLFIRI administration and according to specific instructions on dose-delays and dose-reductions provided in [Table 6](#).

Table 6 Sym004 Dose-Reduction for Grade 3 Skin Toxicity

Skin Toxicity Grade 3	Sym004 Immediate Action	Outcome Improvement	Sym004
First occurrence	Delay dose	Yes, Grade 2	Reduce by 3 mg/kg
		Yes, Grade ≤1	Continue at same dose
		No	Discontinue
Second occurrence	Delay dose	Yes, Grade 2	Doses at 9 mg/kg or above: Reduce by 3 mg/kg Dose at 6 mg/kg: Reduce by 1.5 mg/kg
		Yes, Grade ≤1	Continue at same dose
		No	Discontinue
Subsequent occurrences	Delay dose	Yes, Grade 2	Doses at 9 mg/kg or above: Reduce by 3 mg/kg Dose at 6 mg/kg: Reduce by 1.5 mg/kg Dose at 4.5 mg/kg: Discontinue
		Yes, Grade ≤1	Continue at same dose
		No	Discontinue

In case of a Grade 2 skin toxicity, which is locally debilitating for the patient, the guidelines outlined in [Table 6](#) above may be followed at the Investigator’s discretion.

In the occurrence of fissures unresponsive to intensive therapeutic treatment as specified in [Table 15](#), the dose of Sym004 should be delayed or reduced. The need for > 2 week dose delays or dose-reduction should be discussed with the Sponsor or designee if adequate improvement is not seen after the initial delay.

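### Table 15 lists no action with Sym004 for fissures of any grade at Steps 1 and 2, although Section 7.1.5.2 requires a pause for every Grade 3 skin toxicity; no sentence says which governs a Grade 3 fissure

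*Protocol*

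**What the plan says.** Section 7.1.5.2 gives the dosing rule: "The infusion of Sym004 must be paused in the event of a Grade 3 skin toxicity". No type of skin toxicity is exempted. The pause is made "by delaying the dose of Sym004 resulting in a period of approximately 28 days between 2 Sym004 administrations". Table 6 then sets the next step at first occurrence: resume at the same dose if the event falls to Grade 1 or lower, reduce by 3 mg/kg if it falls to Grade 2, and discontinue if it does not improve.

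The same section closes with a paragraph that carries no grade. It opens "In the occurrence of fissures unresponsive to intensive therapeutic treatment as specified in", with a reference to Table 15, and calls for a delay or reduction in that event. Any longer delay or further step "should be discussed with the Sponsor or designee if adequate improvement is not seen after the initial delay".

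Section 7.2.4 introduces its tables as "Recommendations for management of Grade 1 to 3 Sym004 induced skin toxicities, i.e. rash, xerosis, paronychia, pruritus, photosensitivity and fissures". Tables 10 to 14 are graded, and each has a Grade 3 row that delays Sym004 and refers to Table 6. Table 15 has no grades. Its lead-in reads "Should fissures begin to form, a stepwise approach outlined in", and then names this table. Step 1 starts at first occurrence and Step 2 is entered "If no improvement after 2 weeks from initiation of Step 1"; in both, the Sym004 column says that no action is taken. Step 3, entered "If no improvement after 2 weeks from initiation of Step 2", is the first to delay the drug.

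**The concern.** Section 3.2.4.1 counts fissures among the anti-EGFR skin toxicities. Section 9.2.3 supplies a general severity scale where CTCAE has no specific one, so a fissure can be Grade 3. For such a patient the two sections give different instructions at the next infusion: 7.1.5.2 withholds it, while Table 15 as written leaves it in place. Only Grade 4 is settled, by withdrawal from Sym004.

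The fissure paragraph in 7.1.5.2 makes the gap harder to dismiss, because it ties delay or reduction to failure of Table 15 treatment. A site could take it as a specific rule that replaces the general one. What is at stake is dosing safety: a patient whom the protocol says must be paused could be infused.

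**Working it through.** **Inputs.** Sym004 is given every 14 days (Section 5.3.3). The Grade 3 pause leaves about 28 days between administrations (7.1.5.2), so 28/14 − 1 = 1 infusion is skipped. Table 15 Steps 1 and 2 last 14 + 14 = 28 days, so 28/14 = 2 infusions fall due before Step 3, one in each step. Let D be the assigned dose in mg/kg. The comparison assumes a first Grade 3 occurrence, nominal visit days, and a site that follows Table 15 in place of 7.1.5.2.

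**Onset found at the pre-dose examination.** Call that day Day 0; the last infusion was on Day −14.
- 7.1.5.2 and Table 6: Day 0 is withheld and resumption is due on Day −14 + 28 = Day 14.
- Table 15: Day 0 is given. Step 2 would begin on Day 14, the same day as the Table 6 resumption.
- Improved by Day 14: Step 2 is not entered and Table 15 does not address the Day 14 dose. Excess = D − 0 = D.
- Not improved on Day 14: Table 15 leaves the Day 14 infusion in place and Table 6 discontinues. Excess = 2D − 0 = 2D.

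**Onset 7 days after an infusion.** The last infusion is Day 0 and onset is Day 7.
- 7.1.5.2 and Table 6: Day 14 is withheld and resumption is due on Day 28, which is 28 − 7 = 21 days after onset.
- Table 15: Day 14 is given in Step 1. Step 2 begins on Day 7 + 14 = Day 21 if there is no improvement, and Day 28 is then given at D.
- Improved by Day 21: Step 2 is not entered. Excess = D, as above.
- Unimproved on Day 21: the excess depends on the state at Day 28.

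| State at Day 28 | Table 15 | Table 6 | Excess | D = 12 |
|---|---|---|---|---|
| Grade 1 or lower | 2D | D | D | 12 mg/kg |
| Grade 2 | 2D | D − 3 | D + 3 | 15 mg/kg |
| No improvement | 2D | 0 | 2D | 24 mg/kg |

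In the first two rows the excess is one infusion (two against one), and in the second row the resumed dose is also 3 mg/kg lower under Table 6. Only the third row gives an excess of two infusions.

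**Definitions.** Table 6 counts a fall to Grade 2 or lower as improvement. Table 15 does not define the word. A fissure that is smaller but still Grade 3 could count as improved under Table 15 and as unimproved under Table 6, so the two conditions cannot be treated as the same.

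**The case against.** The strongest reply is that the governing rule is already written. Section 7.1.5.2 is the dose-modification section, its Grade 3 pause is mandatory, and it exempts nothing. Section 7.2.4 only makes recommendations. Read in order, 7.1.5.2 deals with Grade 3, then debilitating Grade 2, then fissures that resist treatment, so its last paragraph looks like an added trigger for fissures not already paused. Table 15 starts when fissures begin to form, which suggests early lesions, and its no-action entry may mean only that the step itself triggers no dose change. Section 7.1.5 also directs Grade 3 skin toxicity to 7.1.5.2.

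There are safeguards as well. The skin is examined before dosing on Day 1 and Day 15 of each cycle (8.2.7), a dermatologist is strongly recommended at Grade 3 (7.2.4), and the Investigator must withdraw treatment for any adverse event judged to require it (6.3.1).

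Most of this stands. The mandatory rule is the better reading, and unnoticed dosing through a Grade 3 fissure is unlikely. What remains is that the examination finds the fissure without saying whether to infuse. Table 15 uses the same dosing column in which Tables 10 to 14 give explicit dosing instructions, and the subordinate role of the fissure paragraph has to be inferred.

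A reader might go further and infer that the protocol directs sites to dose through Grade 3 fissures, or that the excess is always two infusions. The text supports neither. The first ignores the unexempted pause in 7.1.5.2. The second holds only when the fissure is unimproved at both decision points, which differ in timing when onset falls between infusions and differ in how improvement is judged.

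**Conclusion.** The point holds as a low-priority safety clarification. Table 15, followed as written for a Grade 3 fissure, leaves in place at least one infusion of D mg/kg that 7.1.5.2 withholds. The excess is two infusions only if there is no improvement both at entry to Step 2 and at the Table 6 resumption point. These sizes are conditional on a site following Table 15 over the mandatory rule.

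How many patients could be affected is unknown, because no rate of Grade 3 fissures is given. The 33.3% and 41.2% in Section 3.2.4.1 (12 and 18 mg/kg every 2 weeks) cover all Grade 3 skin toxicities in patients previously given anti-EGFR antibodies and cannot stand in for it.

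A reader might also infer an effect on dose-finding. The documents do not support that: under 9.5.1 a related Grade 3 non-hematologic toxicity in the observation period is dose-limiting regardless of duration, and fissures are not among the exceptions. Accrual has stopped (5.5), so the effect is confined to dosing safety in patients still on Sym004. Sample size and analysis are untouched.

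**What to change.** In Table 15, limit the no-action Steps 1 and 2 to Grade 1–2 fissures. Add a Grade 3 row that delays Sym004 and refers to Table 6 while the topical treatment continues, as Tables 10 to 14 do. In 7.1.5.2, state that the fissure paragraph adds a trigger for persistent fissures below Grade 3 and does not replace the Grade 3 pause. If the sponsor does intend to exempt fissures from that pause, 7.1.5.2 should say so explicitly.

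The cost is one table row, a grade limit and one sentence. Section 17 requires Sponsor agreement and Ethics Committee approval, so the change could travel with another amendment. Data collection and analysis do not change.
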